Investigators must discuss the choice of the follow-up HAART regimen with the Medical Monitor prior to initiating the new regimen with the participant. HAART therapy should be initiated within 8 weeks after the last Q2M injection, however if withdrawn due to virologic failure, HAART should be initiated as soon as virologic failure is confirmed. Discuss with medical monitor. The LTFU will begin the day of the last CAB LA and/or RPV LA dose and continue for 52 weeks. These participants will not complete a Withdrawal visit, but will instead move directly into the LTFU as per the Time and Events Schedule. In addition, for participants who withdraw during the LTFU, the final visit will be considered the study withdrawal visit.

Participants will be assessed with clinic visits at months 1, 3, 6, 9, and 12 during the LTFU Phase. Female participants of child bearing potential must continue to use adequate contraception methods for the entire year of follow up.

In order to assure that participants have access to HAART during the LTFU, ViiV Healthcare may supply HAART regionally or reimbursement will be provided as needed during this phase. The LTFU Phase may be shortened or terminated at any time during

the study for various reasons, e.g., better understanding of risks of development of resistance as CAB and RPV exposures decline, end of study timings, etc.

This phase is considered study participation and participants will be followed on study during this time. A withdrawal visit is not required for participants who do not complete the LTFU Phase. The participants' last on study visit will be considered as their withdrawal visit.

Dose Modifications

No dose reductions, modifications, or changes in the frequency of any components of each regimen will be allowed during the study beyond what is allowed within the protocol or directly approved by the study Medical Monitor. Protocol waivers or exemptions are not allowed. Therefore, adherence to the study design requirements is essential and required for study conduct.

[figure not shown]

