Venipuncture	Participants will be required to have blood samples taken. Risk of bruising, and rarely, infection	
 • Trained personnel will perform venipuncture
Risks of ECG pad removal	Some discomfort and rash may occur where the ECG pads are removed.	
 • ECGs will be conducted by appropriately trained personnel and effort made to minimize contact time for application of the pads.
Risk of Treatment Failure	This study employs a novel 2 drug LA ART maintenance regimen for the treatment of HIV-1 infection that remains experimental. Both IM CAB and RPV have demonstrated antiviral activity in large clinical studies and the two-drug combination has demonstrated sustained antiviral activity in studies, LA116482 and 200056, however the efficacy of Q8W v Q4W dosing remains	
 • Viral loads and CD4+ cell counts will be closely monitored throughout the study (maintenance and extension phases), allowing for early detection of failing treatment. Where confirmed virological failure occurs, participants would be discontinued from study drugs and transferred to an oral

Potential Risk of Clinical Significance	Summary of Data/Rationale for Risk	Mitigation Strategy
	
under evaluation.
 
Doses of the CAB LA and RPV LA have been selected to achieve exposures that are expected to maintain virologic efficacy on the basis of available data with the oral and LA formulations.
 
Due to administration error, it is possible that a participant could receive an inadequate dose of CAB LA or RPV LA. Sub-therapeutic concentrations of either CAB LA or RPV LA could lead to virologic failure and possibly the development of viral resistance.
	
HAART regimen.
 
 Plasma samples will be collected throughout the Maintenance Phase for determination of CAB and RPV concentration and possible pharmacokinetic correlation with virologic response.

DTG + RPV

For safety and risk mitigation for DTG +RPV, you may also refer to the Juluca prescribing information [[Juluca Prescribing Information, 2017](#)].

Potential Risk of Clinical Significance	Data/Rationale for Risk	Mitigation Strategy ^a
Commercial Juluca [DTG and RPV] Refer to IBs for additional information		

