7. DISCONTINUATION OF STUDY INTERVENTION AND PARTICIPANT DISCONTINUATION/WITHDRAWAL

A participant may withdraw consent and discontinue participation in this study at any time at his/her own request. The investigator may also, at his or her discretion, discontinue the participant from participating in this study at any time (e.g., safety, behavioral or administrative reasons). If a participant withdraws from the study, he/she may request destruction of any samples taken, and the investigator must document this in the site study records. Withdrawn participants will not be replaced.

All participants who discontinue prematurely from the study, irrespective of arm, will be asked for additional information to establish the reason for withdrawal.

Participants are not obligated to state the reason for withdrawal. However, the reasons for withdrawal, or failure to provide a reason, must be documented by the Investigator on the Completion/Withdrawal section of the electronic case report form (eCRF). Every effort should be made by the Investigator to follow-up participants who withdraw from the study.

Participants may have a temporary interruption to their study intervention for management of toxicities.

Participants may be prematurely discontinued from the study intervention for any of the following reasons:

- Adverse event / Serious adverse event
- Protocol deviation
- Intolerability of injections
- Participant lost to follow-up
- Participant or Investigator non-compliance;
- Termination of the study by the Sponsor
- At the request of the participant, Investigator, GSK or ViiV Healthcare;
- The participant requires concurrent prohibited medications during the course of the study. The participant may remain in the study if in the opinion of the Investigator and the medical monitor; such medication will not interfere with the conduct or interpretation of the study or compromise the safety of the participant.

Participants must be discontinued from study intervention for any of the following reasons:

- Virologic withdrawal criteria as specified in Section 7.1.3 are met;
- Participant requires substitution of ART;
- Participant requires substitution or dose reduction of CAB LA, RPV LA (oral bridging supply and potential for a second loading dose may be permissible following discussion with the Medical Monitor) and oral DTG + RPV.
- Liver toxicity where stopping criteria are met and no compelling alternate cause is identified (see Section 7.1.1);

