7.1.1.1. Liver Chemistry Stopping Criteria, Participant Management and Follow-up

Participants who develop ALT ≥ 5 xULN must be followed weekly until resolution or stabilization (ALT < 5 xULN on 2 consecutive evaluations).

When any of the liver chemistry stopping criteria is met, do the following:

- Immediately hold IP. If on LA therapy, **do not** administer another injection until approval is received from the ViiV Safety and Labelling Committee.
- Report the event to the Medical Monitor within 24 hours of learning its occurrence.
- Complete the liver event eCRF and SAE eCRF, where applicable.
- Complete the liver imaging and/or liver biopsy eCRFs if these tests are performed.
- Perform liver event follow up assessments (described below), and monitor the participant until liver chemistries resolve, stabilize, or return to Baseline values as described below.
- Make every reasonable attempt to have participants return to clinic within 24 hours for repeat liver chemistries, liver event follow-up assessments (see below), and close monitoring.
- A specialist or hepatology consultation is recommended.
- Monitor participants twice weekly until liver chemistries (ALT, AST, alkaline phosphatase, bilirubin) resolve, stabilize or return to within Baseline values.

Make every attempt to carry out the **liver event follow-up assessments** described below:

- Viral hepatitis serology including:
 - Hepatitis A immunoglobulin M (IgM) antibody;
 - Hepatitis B surface antigen (HBsAg) and Hepatitis B Core Antibody (IgM);
 - Hepatitis C RNA;
 - Hepatitis E IgM antibody;
 - Cytomegalovirus IgM antibody;
 - Epstein-Barr viral capsid antigen IgM antibody (or if unavailable, obtain heterophile antibody or monospot testing);

- Syphilis screening;
- Drugs of abuse screen including alcohol;
- Serum acetaminophen test (N-acetyl-para-aminophenol [APAP] adduct test). The site must contact GSK when this test is required. Please refer to the central laboratory manual.

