7.1.5.3. Confirmed Virologic Failure

Participants with CVF must be discontinued from study intervention. However, participants who have received at least one dose of CAB LA or RPV LA prior to confirming virologic failure will remain in the study on oral HAART in the LTFU Phase.

A plasma sample from the suspected virologic failure visit as well as Day 1 (if baseline HIV-1 RNA level ≥ 200 c/mL) will be sent for genotypic and phenotypic resistance testing and the result made known to the Investigator when available. A plasma sample from the confirmation visit will be obtained for storage. This sample may be used for possible future analyses, e.g., for genotypic and phenotypic analyses of participants who experience virologic failure.

For all participants who meet CVF, baseline and suspected virologic failure plasma samples with HIV-1 RNA level ≥ 200 c/mL will be analyzed in an attempt to obtain genotype/phenotype data on as many samples as possible. Plasma samples for storage will also be obtained at unscheduled visits including confirmation of CVF. Participants may continue to receive study drug at the discretion of the investigator until results of resistance testing are available at which time the participant must be discontinued from the study. Even if genotype/phenotype data cannot be generated, participant must also be discontinued from the study intervention.

If a participant is prematurely discontinued from the study intervention, the investigator must make every effort to perform the Withdrawal Visit evaluations outlined in the Time and Events. These data will be recorded as they comprise essential evaluations needed to be done before discharging any participant from the study.

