8.10.1. HIV-1 Polymerase Viral Genotyping and Phenotyping

Participants meeting confirmed virologic failure will have plasma samples tested for HIV-1 PRO and RT genotype and phenotype and HIV-1 integrase genotype and phenotype from samples collected at the time of meeting suspected virologic failure; these results will be reported to the investigator as soon as available to provide guidance for election of an alternative regimen.

[figure not shown]

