#### NOTES:

- T = Table, F = Figure, L = Listing, Y = Yes display generated.
- Summary = Represents TF related to any summaries (i.e. descriptive statistics) of the observed raw data.
- Individual = Represents FL related to any displays of individual participant observed raw data.
- 1. For the CVF as indicated by two consecutive plasma HIV-1 RNA levels ≥200 c/mL after prior suppression to <200 c/mL, the first visit of these two consecutive visits is defined as 'the suspected visit', and the 2nd one is the confirmed visit. Sample used for resistance testing is taken at the suspected visit, and only tested once a participant confirms virological failure at a subsequent visit. If the test fails with the sample at the suspected visit, we will just report it as 'no data'. The sample from the confirmed visit may be used for exploratory analyses.

- No. and percentage of participants with IN resistance mutations or major mutations in the classes of NNRTI, NRTI, PI, respectively, as defined in Section 12.6.6.
- 3. Separate outputs by phenotypic susceptibility and by number of drugs to which participants are phenotypic resistant or partial sensitive or sensitive.
- 4. Fold change to CAB and RPV will be included in the listing for viral load, genotypic and phenotypic data for participants with genotype and/or phenotype data for CVF and non-CVF participants.

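### Protocol 7.1.5.3 does not exclude a further CAB LA or RPV LA injection after confirmed virologic failure while resistance results are awaited, which is out of line with Sections 1.1, 4.2.3 and 2.3.1

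*Protocol*

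**What the plan says.** Protocol Section 7.1.5.3 opens with a rule that carries no timing: "Participants with CVF must be discontinued from study intervention". Its second sentence is specific to LA-exposed participants and keeps them in the study, on oral HAART in the long-term follow-up (LTFU) phase. Two paragraphs later comes the permission: "Participants may continue to receive study drug at the discretion of the investigator until results of resistance testing are available". That sentence ends by requiring discontinuation from the study when the results arrive. Section 6.1 counts the LA forms of cabotegravir and rilpivirine among the study drugs.

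Two other places deal with LA participants at the same moment.

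- Section 1.1, repeated in 4.2.3 under a title restricted to the IM regimen, gives a general limit of 8 weeks after the last injection for starting HAART. It then adds: "however if withdrawn due to virologic failure, HAART should be initiated as soon as virologic failure is confirmed. Discuss with medical monitor".
- Section 2.3.1, on the risk of treatment failure with the LA regimen, gives the mitigation: "Where confirmed virological failure occurs, participants would be discontinued from study drugs and transferred to an oral" HAART regimen.

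Two places describe the resistance test. SAP Section 10, Table 5 note 1, says that the sample from the suspected-failure visit is "only tested once a participant confirms virological failure at a subsequent visit". Protocol Section 8.10.1 says that results go to the investigator "as soon as available to provide guidance for election of an alternative regimen".

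**The concern.** Because the sample is tested only after failure is confirmed, the period covered by the permission always runs past confirmation. Sections 1.1, 4.2.3 and 2.3.1 place the switch to HAART at confirmation. A site treating an LA participant therefore has one section pointing to HAART now and another allowing study drug to go on, with nothing to say which governs.

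An LA injection cannot be withdrawn. Section 2.3.1 notes that residual drug can persist for more than a year in some participants and that resistance can develop during that time. Section 4.2.3 gives avoidance of selective pressure as the reason for HAART cover after LA dosing. A further dose of a regimen already confirmed to be failing works against that aim. It would also restart the 52-week LTFU clock, which runs from the last LA dose.

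**Working it through.** No sample size, power or precision figure is involved. The check has two parts.

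**1. Which passages conflict for an LA participant**

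| Place | Action | Timing | Conflict with the permission? |
|---|---|---|---|
| 1.1 and 4.2.3 | Start HAART | At confirmation (worded as a recommendation, for those withdrawn) | Yes |
| 2.3.1 | Stop study drugs, move to oral HAART | At confirmed failure | Yes |
| 7.1.5.3, opening sentence | Discontinue | None given | Not firm |
| Section 7, mandatory list | Discontinue if "Virologic withdrawal criteria as specified in Section 7.1.3 are met" | None given; 7.1.3 says only that central-laboratory values count | Not firm |

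**2. When an injection could fall inside the permitted period**

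Inputs:

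- Target days follow (m − 1) × 30 + 1 (SAP 12.3.1): Day 1 = 1, Month 2 = 31, Month 4 = 91, Month 6 = 151.
- The planned interval is 60 days (SAP 12.6.2).
- The dosing window is −7 to 0 days at Month 2 and ±7 days afterwards, around dates projected from Day 1 (Protocol 4.2.2, 6.8.1 and 6.8.1.1).

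Let *i* be the days from the suspected-failure visit to the next injection, assuming an injection was given at that visit.

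- From Month 4 on: nominal 151 − 91 = 60. Extremes are 60 − 14 = 46 and 60 + 14 = 74.
- From Month 2: nominal 91 − 31 = 60. Month 2 can fall on days 24 to 31 and Month 4 on days 84 to 98, giving 84 − 31 = 53 to 98 − 24 = 74.
- From Day 1: nominal 31 − 1 = 30, and 24 − 1 = 23 at the earliest.

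Let *c* be the days from the suspected-failure visit to confirmation, and *T* the days from confirmation to the resistance result. An injection falls in the permitted period only if *c* < *i* < *c* + *T*. An injection before confirmation comes under 7.1.5.2 instead.

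The documents give no unconditional value for *c*. Section 7.1.5.2 mentions 2 to 4 weeks, but after an illness resolves or therapy resumes. I assume 14 to 28 days. They give no value for *T*. The turnaround would have to exceed *i* − *c*:

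| Suspected failure at | *i*: earliest / nominal / latest | *T* must exceed, *c* = 14 | *T* must exceed, *c* = 28 |
|---|---|---|---|
| Month 4 or later | 46 / 60 / 74 | 32 / 46 / 60 | 18 / 32 / 46 |
| Month 2 | 53 / 60 / 74 | 39 / 46 / 60 | 25 / 32 / 46 |
| Day 1 | 23 / 30 / – | 9 / 16 / – | before confirmation / 2 / – |

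The Day 1 row is an edge case. Entry requires HIV-1 RNA below 50 c/mL at Week 300 (on a single approved repeat if needed) and excludes any value of 200 c/mL or more in the last 6 months of LATTE. Section 7.1.5.3 does, however, provide for a baseline value at or above 200 c/mL.

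**Context on frequency.** Section 2.2 reports 2 protocol-defined failures on Q8W dosing in LATTE-2 through Week 96, and Section 4.4.1 gives N = 115. That is 2/115 = 1.7% (exact 95% CI 0.2% to 6.1%). If all of about 100 participants chose LA, an upper-bound assumption, 100 × 1.7% is about 2 participants (0 to 6 over the interval).

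**The case against.** The strongest reply is that the permission was never meant for LA participants. The second sentence of 7.1.5.3 already sends them to oral HAART, and the ending of the permission, discontinuation from the study, fits only the oral arm because LA participants stay on for LTFU. This stands as evidence of intent. It makes the text ambiguous; it does not close the gap, because the sentence is not limited by arm and Section 6.1 includes the LA products.

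A reader might go further and infer that 7.1.5.3 plainly authorises injections after failure, or that it contradicts its own opening sentence and the Section 7 list. The documents do not support either. Those two places set no timing, so a short grace period ending in mandatory discontinuation is compatible with them.

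Existing controls also count. The medical monitor is to be consulted (4.2.3, 6.8). The general 8-week limit for HAART is 56 days, before the 60-day nominal injection date. But that limit is for participants who have stopped the regimen, and the earliest in-window injection (day 46 or 53) precedes it. Monitor contact lowers the risk without forbidding the dose.

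Waiting for resistance results has a sound purpose under 8.10.1. That supports delaying the final choice of HAART, not giving another injection.

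The liver rule in 7.1.1.1 tells sites not to "administer another injection until approval is received from the ViiV Safety and Labelling Committee". It shows that the protocol can state an injection bar, but liver events are a hold with a possible restart and CVF is not. Its absence for CVF does not show a permissive design.

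**Conclusion.** The point holds as an ambiguity that should be removed. For LA participants, 7.1.5.3 is inconsistent with 1.1/4.2.3 and with the mitigation in 2.3.1, and nothing in the documents bars a further CAB LA or RPV LA injection once CVF is confirmed.

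Its practical size is small and uncertain. An extra injection is possible only when the due date lies between confirmation and the resistance result. At the nominal 60-day interval, and with confirmation assumed at 14 to 28 days, that needs a turnaround of more than 32 to 46 days from confirmation. A reader might infer that extra injections are likely. With no turnaround stated and few failures expected, the documents do not support that. What gives the point weight is that such a dose could not be reversed. Severity is minor to moderate, and the estimation of the primary endpoint is not affected.

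**What to change.** In Section 7.1.5.3:

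1. State that no further CAB LA or RPV LA injection is given once CVF is confirmed.
2. Limit the permission to continue until resistance results to oral DTG + RPV. The two firm inconsistencies concern the LA regimen, so keeping the permission for the oral arm does not revive them.
3. For LA participants, cross-refer to 4.2.3 for the start of HAART and entry to LTFU. This also settles the mismatch between leaving the study and staying in it for LTFU.

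The change adds no procedures. It is a protocol amendment, so it needs IRB/IEC approval (Section 12.2.1). The first HAART regimen may be chosen before the resistance results and need adjusting when they arrive; item 1 alone does not carry that drawback.

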8. STUDY ASSESSMENTS AND PROCEDURES

Protocol waivers or exemptions are not allowed with the exception of immediate safety concerns. Therefore, adherence to the study design requirements, including those specified in the Time and Events Table, are essential and required for study conduct.

This section lists the procedures and parameters of each planned study assessment. The exact timing of each assessment is listed in the Time and Events Table (Section 8.1).

The following points must be noted:

- If assessments are scheduled for the same nominal time, THEN the assessments should occur in the following order:
 1. 12-lead ECG
 2. vital signs
 3. blood draws

Note: The timing of the assessments should allow the blood draw to occur at the exact nominal time.

- The timing and number of planned study assessments, including safety, pharmacokinetic, pharmacodynamic/biomarker assessments may be altered during the course of the study based on newly available data (e.g., to obtain data closer to the time of peak plasma concentrations) to ensure appropriate monitoring.
- The IRB/independent ethics committee (IEC) will be informed of any safety issues that require alteration of the safety monitoring scheme or amendment of the Informed Consent Form.

8.1. Time and Events Table

8.1.1. Time and Events Table for CAB LA + RPV LA Q2M Administration

Procedures Q2M	Day 1 ^a	Month												WD ^{l,m}	
		2 ^o	4	6	8	10	12	14	16	18	20 ^b	22 ^b	24		26
Written Informed Consent	X														
Demography	X														
Eligibility Verification	X														
Physical Exam	X														
Medical History	X														
CDC Classification	X														
Rapid Plasma Reagin (RPR)	X														
Symptom Directed Physical Exam, ISR and Medical Assessment ^c	X	X	X	X	X	X	X	X	X	X	X	X	X	X	X
Vital Signs (blood pressure [BP], heart rate [HR]) ^d	X	X	X		X		X		X		X		X		X
Weight, Height & body mass index (BMI) ^e	X	X	X		X		X		X		X		X		X

Procedures Q2M	Day 1 ^a	Month												WD ^{f,m}	
		2 ^o	4	6	8	10	12	14	16	18	20 ^b	22 ^b	24		26
HIV Associated Conditions, AE and SAE Assessments, Con Meds	X	X	X	X	X	X	X	X	X	X	X	X	X	X	X
12-Lead ECG ^f	X						X								X
Clinical Chemistry and Hematology	X	X	X		X		X		X		X		X		X
Pregnancy Testing (U)rine or (S)erum ^g	U	U	U	U	U	U	U	U	U	U	U	U	U	U	U
HIV-1 RNA and sample for storage ^h	X	X	X	X	X	X	X	X	X	X	X	X	X	X	X
CD4+	X	X	X		X		X		X		X		X		X
Urinalysis	X														X
Fasting Glucose, Cholesterol (Total, high density lipoprotein [HDL] and low density lipoprotein [LDL]) and Triglycerides ⁱ	X						X						X		X
Prothrombin time (PT)/ Partial Thromboplastin Time (PTT)/international normalized ratio (INR)	X														X

Procedures Q2M	Day 1 ^a	Month												WD ^{i,m}	
		2 ^o	4	6	8	10	12	14	16	18	20 ^b	22 ^b	24		26
PK Diary (D)ispensation and (R)evuew	R														
PK Sample (S)torage j	S						S								S
LA Study intervention Administration ^k	X	X	X	X	X	X	X	X	X	X	X	X	X	X	
HIVTSQc							X								X
HIVTSQs	X			X			X								X
HIVDQoL	X			X			X								X
Preference							X								
Reason for Switch	X														
Participant Visit Reminder Contact	X	X	X	X	X	X	X	X	X	X	X	X	X	X	
Participant Contact Detail Confirmation	X	X	X	X	X	X	X	X	X	X	X	X	X	X	

See footnote "b" for continuation of visit schedule after Month 26. Continue until either locally approved and commercially available, the participant no longer derives clinical benefit or meets a protocol-defined reason for discontinuation or until development is terminated.

- a. The Day 1 visit will take place during Week 312 (or Week 324 in the event of unavoidable delays) of the LATTE study, the participant's last week on study. LATTE participants eligible for POLAR study dosing will take final dose of CAB 30 mg + RPV 25 mg in the clinic within 2 hours of the Q2M IM regimen. See Section 6.1 for IM dosing administration as loading doses are required. (Day 1=1st loading dose; Month 2=2nd loading dose)
- b. Continue this pattern for visits for the remainder of the study. For example, Month 28 will be conducted just like Month 20, Month 30 will be conducted just like Month 22 and so on.
- c. Physical exams should be conducted as part of normal routine clinical care but data will not be collected in the eCRF. Medical assessments include any decisions the study staff must make for participant management.
- d. Measure vital signs after about 5 minutes of rest in a semi-supine position.
- e. Height collected at Day 1 only.
- f. On Day 1, ECGs should be performed in triplicate at least 5 minutes apart and following 5 minutes of rest in a semi-supine position within 1 hour prior to first dose. Also on Day 1, a 2-hour post dose ECG will be performed for all participants. The 2-hour post dose ECG on Day 1 can also be used for the LATTE Week 312 (or Week 324, if needed) visit. ECG evaluations at other visits should be obtained after dosing, preferably 2-4 hours post dosing.
- g. A (-) urine pregnancy test is required prior to any injection and as required by medical monitor after a treatment interruption. A (+) urine test should be confirmed with a stat serum test. If (+), participant will need to be WD.
- h. Plasma for storage samples are collected for possible future analyses, back-up in cases of loss/damage in transit and geno/pheno analyses for virologic failures.
- i. Fast overnight; however, a minimum of a 6 hour fast is acceptable.
- j. Take PK samples pre-dose.
- k. Q2M Injections are 1 x CAB LA 600 mg IM + 1 x RPV LA 900 mg IM. If possible, injections should be spaced approximately 2 cm from one another and from the site of any previous injection and or any injection site reaction. Bring RPV LA to approximately room temperature prior to injecting. Time and location of injection (right or left) as well as needle length used will be collected in the eCRF. **IM dosing is expected to occur during the month in which the participant's projected visit falls (as according to the Day 1 visit). An additional (+ or -) 7 day window from date of projected visit is stipulated for IM dosing. All decisions regarding dose interruption/ resumption must be discussed with the medical monitor in advance.**
- l. Or Long-Term Follow Up
- m. Follow Up Visit - Conduct ~4 weeks after the last dose of IP if not entering Long-Term Follow Up and only if the participant has ongoing AEs or lab abnormalities at the last on-study visit. May be conducted by telephone.

